**Specific Aim 3 (exploratory): To measure metabolite changes induced by T in infants with XXY.**

**Hypothesis:** Circulating metabolites involved in energy metabolism, specifically long chain acyl-carnitines (LCAC) and branched-chain amino acids (BCAA), will be lower due to improved mitochondrial function in T treated boys; T will favorably alter pathways involved in energy metabolism. **Approach:** LCAC and BCAA will be quantified at baseline and 12 weeks in the first 20 subjects. An unbiased platform of over 4,000 metabolites will also be performed to identify pathways that are differentially regulated with T treatment.

[figure not shown]
Assessing short-term safety and efficacy of T treatment in infants with XXY will provide the first evidence for establishing standard of care practices, with a planned extension for long-term outcomes. These results will generate preliminary data on mechanisms of the effects of T during the critical mini-puberty period for the development of future work, such as sex steroid-induced epigenetic modifications. Mentors with expertise in neurodevelopment, cardiometabolic outcomes, metabolomics, and clinical trials will optimize career development and foster expertise in gonadal and cardiometabolic function in children with sex chromosome aneuploidies.

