## IV. Research Methods

### A. Outcome Measure(s):

#### Primary for Specific Aim 1

Change in %BF z-scores from baseline to 12 weeks (per PeaPod)

#### Primary for Specific Aim 2

Change in motor composite percentile on the AIMS assessment from baseline to 12 weeks

#### Primary for Specific Aim 3

Change in C14:1 long chain acylcarnitine (LCAC) from baseline

**Secondary outcomes:** Change in %BF z-scores from 12 to 24 weeks; change in anthropometric measurements from baseline to 12 and 24 weeks; change in gross and fine motor scaled scores from the PDMS; cognitive and language scores on the Bayley; adaptive functioning from the ABAS; serum hormones, lipids, BCAA, LCAC, and pathway analysis of untargeted metabolomics; urine metabolites; and number and type of adverse events.

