### C. Study Design and Research Methods

**Overall study design.** TESTO is a randomized controlled trial assessing the efficacy and safety of T injections in infants with a prenatal diagnosis of XXY. Body composition, neurodevelopment, serum hormones, safety parameters, and metabolomics will be assessed at baseline, 12 and 24 weeks into the

study. Infants will be randomized 1:1 to receive T vs placebo for the first 12 weeks of the study with the primary outcomes assessed after 12 weeks (Figure 5). The second half of the study will cross the treatment groups allowing us to evaluate if timing makes a difference in response and if initial benefits are sustained. This plan will optimize enrollment, as many parents will only participate if their son will get treatment, and allow us to maintain the blinded design.

**Setting.** The study will be conducted at Children’s Hospital Colorado (CHCO) in the outpatient Pediatric Clinical Translational Research Center (CTRC). CHCO is home to the eXtraordinary Kids Clinic, the first comprehensive interdisciplinary clinic for sex chromosome aneuploidies. The unique collaborative model and our expertise has led to national referrals and a high demand for clinical evaluations. We have successfully recruited hundreds of boys with XXY to participate in longitudinal and interventional research studies through close collaboration with family support groups and national/international experts in XXY. Our investigative team has expertise in child development, infant body composition, childhood disorders of insulin resistance, metabolomics, clinical trial recruitment, robust data acquisition and data analysis, making this the ideal setting.

[figure not shown]

Figure 5. Overall Study Design

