**Consent.** When a child is identified through clinic or other method identified above, a member of the study team will contact the parent to inform them of the opportunity to participate in a study. In many cases, the parents will contact the PI, PRA or genetic counselor of the eXtraordinary Kids Clinic after hearing about the study from one of the above sources. Prior to any information being collected, verbal consent to ask questions pertaining to the inclusion/exclusion criteria will be obtained. A member of the study team will describe the study and will offer to email/mail the consent form to the parents so the parents have ample time to review prior to deciding whether to schedule the first visit and enroll in the study.

Prior to any research procedures being performed, a study team member will review the consent form in person in a private location. Both verbal and written consent will be required from a parent or legal guardian to enroll in the study. All of the subjects in this protocol are infants and therefore too young to assent/consent to research participation themselves. To minimize coercion, parents will not be paid for enrolling their child in the study and only reimbursement for reasonable travel will be provided. We will emphasize to parents their child's participation is entirely voluntary and can be withdrawn at any time. As part of the consent process, parents will be asked to summarize the study in their own words to ensure comprehension, and parents will have the opportunity to ask questions. If the consenting parent does not speak English, an interpreter will assist with the consent process and a short-form consent document in the parent's preferred language will be completed. If the consenting parent is blind, illiterate, or with reading limitations, the entire consent form will be read to the subject and witnessed by someone outside of the study team.

**Randomization.** Subjects will be randomized 1:1 using block randomization in groups of 20 to 1) receive T treatment in the first 12 weeks followed by placebo, or 2) placebo for the first 12 weeks followed by T. Investigational Drug Services at CHCO will generate the automated randomization list and dispense the study drug to maintain allocation concealment. All investigators and parents will remain blind to the intervention group.

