For **specific aim 3 (exploratory)**, we will compare C14:1 concentrations (an easily identified LCAC) between treatment groups at 12 weeks using two-sided t-tests, hypothesizing C14:1 will be lower in the T treated group (representing improvement in fatty acid oxidation and energy metabolism). This aim is exploratory; with 10 subjects per group we will have 80% power to detect a difference of 1.3 SD with a two-sided alpha of 0.05. Then, paired t-tests will be used to compare C14:1 before and after T treatment (5 paired samples), with similar power. We will analyze secondary outcomes including other LCAC and BCAA (leucine, isoleucine, and valine) in a similar fashion. Next, we will use principle component analysis on the entire dataset from the comprehensive untargeted analysis to identify patterns and pathways altered with T treatment. The spectra data file from the non-targeted metabolomics panel will be uploaded to MetaboAnalyst, and the software will be used for Metabolite Set Enrichment Analysis as well as Pathway Enrichment Analysis. We will have >80% power to detect at least 2-fold changes between T treated and untreated using a significance level of 0.0001 (less than two false positives based on the conservative Bonferroni correction for multiple comparisons). We will also input the analytes into known KEGG pathways of energy metabolism to look for pathway enrichment.

Table 2. Summary of primary and secondary outcome measures for each Specific Aim (SA).

SA	Primary Outcome	Weeks		Measurement Tool
		12	24	
SA 1: Cardiometabolic	Change %BF z-scores from baseline	X		PeaPod
	Secondary Outcomes			
	Change %BF z-scores from baseline		X	PeaPod
	Change in height, weight, weight-for-length and waist circumference z-scores from baseline	X	X	Physical exam measurements
	Serum leptin, lipids, and insulin	X	X	Immunoassays in CCTSI core laboratory
SA 2	Primary Outcome			

	Change in motor composite from baseline	X		AIMS percentile composite score (all domains)
	Secondary Outcomes			
	Serum LH, FSH, INHB, AMH, E2 and Total T	X	X	Immunoassay and LC/MS ([name] lab)
	Change in gross and fine motor scaled scores	X	X	Scaled scores on all PDMS-2 domains, AIMS
	Cognitive and Language composite scores	X	X	Bayley III: cognitive and language domains
	Adaptive functioning	X	X	ABAS III standard scores
	Number of adverse events	X	X	Verbal questionnaire, parent-report
SA 3: Metabo- Iomics	Primary Outcomes			

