	Change in C14:1 (LCAC) from baseline	X	X	Targeted metabolomics
	Secondary Outcomes			
	BCAA, other LCAC	X	X	Targeted metabolomics
	Pathway analysis	X		Unbiased metabolomics

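### Aim 3 declares a change-from-baseline primary for C14:1 but tests and powers raw 12-week values, and the documents disagree on whether 24-week samples are assayed

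*Combined protocol and SAP*

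**What the plan says.** Four places bear on the Aim 3 primary.

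- **Outcome list (IV.A):** "Change in C14:1 long chain acylcarnitine (LCAC) from baseline", with no time point.
- **Table 2 (IV.F):** "Change in C14:1 (LCAC) from baseline", marked at weeks 12 and 24. The row for BCAA and other LCAC carries both marks too. The Aim 1 and Aim 2 primaries are marked at week 12 only.
- **Analysis text (IV.F):** "we will compare C14:1 concentrations (an easily identified LCAC) between treatment groups at 12 weeks using two-sided t-tests". The power statement follows: "with 10 subjects per group we will have 80% power to detect a difference of 1.3 SD with a two-sided alpha of 0.05". A second test is then added: "Then, paired t-tests will be used to compare C14:1 before and after T treatment (5 paired samples), with similar power". The text specifies no between-group test of change and no 24-week C14:1 analysis.
- **Assay times:** the Aim 3 approach in section I says "LCAC and BCAA will be quantified at baseline and 12 weeks in the first 20 subjects". The overall design paragraph in IV.C says "safety parameters, and metabolomics will be assessed at baseline, 12 and 24 weeks into the" study. The visit schedule in IV.C includes a blood draw at week 24.

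Allocation is also relevant: "Subjects will be randomized 1:1 using block randomization in groups of 20". The first 20 infants therefore give 10 per arm, which matches the power statement.

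**The concern.** The declared outcome and the tested variable are different quantities. A change score, a raw 12-week value and a baseline-adjusted 12-week value all estimate the same treatment difference in a randomised comparison, but with different precision. With 10 infants per arm they can fall on different sides of 0.05. As written, an analyst could cite the outcome list in support of one and the analysis text in support of another, after seeing the data.

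The time point is open in the same way. Table 2 gives the Aim 3 primary two time points. By week 24 both arms have received T, and IV.E acknowledges that the second half has no control group, so a 24-week change cannot supply a T-versus-placebo contrast. Whether the assay will exist at 24 weeks depends on which section is followed.

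**Working it through.** **Inputs.** From IV.F: n = 10 per arm, difference 1.3 SD, two-sided alpha 0.05, power 80%. The correlation r between baseline and 12-week C14:1 is not given. It is an assumption here, shown from 0 to 0.7, with equal SDs at the two visits. The 1.3 SD is first read as the SD of the 12-week values.

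**Step 1: the plan's own figure.** Two-sample t-test, noncentrality 1.3 × √(10/2) = 2.907, 18 df, critical value 2.101. Power is 78.5% (82.8% by the normal approximation). The difference detectable with 80% power is 1.325 SD, which rounds to the stated 1.3. The figure reproduces for raw 12-week values.

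**Step 2: the same difference on the declared change score.** The SD of change is SD × √(2(1 − r)), so the standardised effect becomes 1.3 / √(2(1 − r)), again with 18 df. At r = 0.3, for example, the SD of change is √1.4 = 1.183 and the effect is 1.3/1.183 = 1.10.

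**Step 3: 12-week value adjusted for baseline.** The residual SD is SD × √(1 − r²), with 17 df. The first adjusted column ignores chance imbalance in baseline. The second allows for it approximately by multiplying the variance by 1 + 1/17.

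| r | SD of change | Power, change | Power, adjusted | Power, adjusted, with imbalance |
|---|---|---|---|---|
| 0 | 1.414 | 49% | 78.2% | 75.9% |
| 0.2 | 1.265 | 58% | 79.8% | 77.6% |
| 0.3 | 1.183 | 64% | 81.9% | 79.7% |
| 0.5 | 1.000 | 78.5% | 88.5% | 86.7% |
| 0.7 | 0.775 | 94% | 96.9% | 96.1% |

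Against 78.5% for the raw test, adjustment changes power by −0.3 to −2.6 points at r = 0, by +1.2 to +3.4 at r = 0.3, and by +8.2 to +10.0 at r = 0.5. With imbalance counted, it breaks even between r = 0.2 and r = 0.3.

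**Step 4: when the stated power applies to the declared outcome.** The SD of change equals the 12-week SD only when 2(1 − r) = 1, that is, r = 0.5. Otherwise the 80% carries over only if the 1.3 SD was meant as the SD of change. The plan states neither.

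**Step 5: the paired test.** With 5 pairs and a mean change of 1.3 SD of the differences, the noncentrality is 1.3 × √5 = 2.907 with 4 df, and power is 59%, so it is not similar to 80%. Baseline and 12-week assays in 20 infants would give 10 pairs in the T-first arm, not 5.

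**The case against.** Several points on the other side are fair.

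- **The power arithmetic is correct.** A reader might infer from the mismatch that the 80% is wrong. It is not; it belongs to a different variable from the declared one.
- **A 24-week sample is planned.** A reader of the Aim 3 paragraph alone might conclude that nothing exists at 24 weeks and that the Table 2 marks are a slip. The documents do not support that: IV.C schedules blood at week 24 and places metabolomics there, and IV.D stores plasma for batch analysis. What is unsettled is whether the 24-week sample is assayed, so deleting the marks would choose a side.
- **A 24-week value could be useful.** Aim 1 looks at weeks 12 to 24 within each group to ask whether effects last and whether later T works. C14:1 could serve the same purpose. The problem is only that week 24 sits on a primary row with no analysis described.
- **Change is not wholly unanalysed.** The paired test uses before-and-after values. It is a within-group test, however, and does not estimate the difference between T and placebo.
- **The unadjusted 12-week comparison is valid.** Randomisation makes it unbiased, and if r is near zero it is slightly more powerful than the adjusted one. Adjustment is a choice for precision and does not correct a bias.
- **The aim is labelled exploratory** and uses 20 infants.

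These points limit the consequence. None removes the mismatch between the declared outcome and the only between-group test.

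**Conclusion.** The concern holds as an inconsistency of definition and timing, and it is minor because the aim is exploratory. Aim 3 names one primary variable and tests another, gives that primary two time points, and has conflicting assay times. The stated power is right for raw 12-week values and would apply to the change score only at a correlation of about 0.5, or if 1.3 SD means the SD of change. For a difference of 1.3 SD of the 12-week values, change-score power runs from 49% at r = 0 to 94% at r = 0.7. These figures rest on an assumed correlation and equal SDs at both visits. The documents do not show that 24-week assays are absent, that the sample size calculation is faulty, or that the planned t-test is biased.

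**What to change.** Define the Aim 3 primary as C14:1 at 12 weeks, compared between arms with baseline C14:1 as covariate, and say that the 10-per-group, 1.3 SD power figure refers to unadjusted 12-week values. Bring IV.A, the Aim 3 text in IV.F and Table 2 into line, with week 12 as the only primary time point. Reconcile the assay times in the Aim 3 approach, IV.C and Table 2. If 24-week assays of C14:1, other LCAC and BCAA are intended, list them as secondary and within-group, because both arms have had T by then. In the same edit, correct the number of pairs and the power claim for the paired test. Settle all this before any C14:1 results are seen.

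The cost is wording and one covariate. Baseline C14:1 is already to be assayed, and IV.F already plans a regression of 12-week %BF on baseline %BF. The statistical price is one degree of freedom and up to about 3 power points if the correlation is near zero, against a gain of about 1 to 3 points at 0.3 and 8 to 10 points at 0.5.

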### G. Summarize Knowledge to be Gained:

This will be the largest assessment of cardiometabolic health, neurodevelopment and testicular function biomarkers in infants with XXY to date and the only longitudinal or interventional study. Management of KS in infancy and childhood is particularly important as screening for fetal aneuploidy is becoming standard of care in all pregnancies through non-invasive prenatal testing. Thousands more infants will be diagnosed with KS with very limited evidence-based management guidelines currently available. Providers and parents alike are seeking more information and options to prevent complications and co-morbidities in this condition. Our results will inform the clinical management of testosterone therapy in infants with XXY, with the promise to provide an early intervention during a critical period that may prevent cardiometabolic and neurodevelopment deficits. If testosterone therapy positively effects body composition and development in infants and does not have safety issues, there would be support for giving this therapy as well as doing long-term follow-up studies. If no short-term benefits are shown following testosterone administration, this would provide evidence for not treating these infants. This study also sets up a unique opportunity to evaluate changes in the metabolome in response to exogenous testosterone, revealing underlying mechanisms involved in the regulation of metabolism and neurodevelopmental pathways during a critical period of infancy.

Furthermore, results of this work may be generalizable beyond KS in understanding the understudied relationship of hypogonadism, body composition, and insulin resistance characteristic of obese boys, a problem of increasing significance secondary to the pediatric obesity epidemic. Other hypogonadal populations including Turner syndrome, Prader-Willi syndrome, and Down syndrome, will also benefit from the results of this study as they too have a blunted mini-puberty period of infancy.

**Future Directions.** Based on the metabolomics results from Aim 3, I will seek funding for the targeted and untargeted metabolomics analysis on stored specimens from all subjects in this study and potentially be able to compare to normal control infants and infants with other high risk factors for cardiometabolic dysfunction, such as maternal obesity and diabetes. We will consent for future contact to be able to follow this cohort longitudinally and compare their long-term neurodevelopmental outcomes to infants who do not receive T but have identical services through the eXtraordinary Kids Clinic. Depending on our results, my future R01 proposals may include long term follow up of this cohort and using additional -omic studies to understand the programming mechanisms occurring during the mini-puberty period or other critical times in development. Another future direction is long-term longitudinal assessment of boys with XXY compared to XY controls, evaluating the many covariates (genetic, epigenetic, environment, T treatment, and other interventions) that influence phenotypic variability in XXY. My work will contribute to the development and refinement of evidence-based guidelines to ultimately improve cardiometabolic and neurocognitive outcomes in this population.

